All subjects must receive ciNPT for a duration consistent with the IFU document included with the selected Prevena[™] Dressing but no shorter than five days post-surgery. A maximum duration indicated in the IFU document of the Prevena[™] Dressing applied immediately following surgery is encouraged. The dressing should not be lifted or removed for reasons other than those related to the device such as initial malfunction or leak alarm.

At the end of the ciNPT treatment period, the dressing and unit are to be removed; re-application of the Prevena[™] dressing is prohibited after the treatment period. If continued drainage is determined by the Investigator's visual inspection of the incision at the time of dressing removal, an SSC event should be documented.

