4.11.1.1. SSC Components

1. Superficial Incisional Surgical Site Infection (SSI) involves only skin and subcutaneous tissue of the incision and meets at least one of the following criteria:
 - purulent drainage from superficial incision;
 - organisms identified from an aseptically-obtained specimen from the superficial incision or subcutaneous tissue by a culture or non-culture based microbiologic testing method which is performed for purposes of clinical diagnosis or treatment (e.g., not Active Surveillance Culture/Testing [ASC/AST]);
 - both of the following:
 - superficial incision that is deliberately opened by Investigator and culture or non-culture based testing is not performed, and
 - at least one of the following signs or symptoms:
 - pain or tenderness;
 - localized swelling;
 - erythema; or
 - heat.
 - diagnosis of superficial SSI by the Investigator.
2. Deep Incisional SSI which involves deep soft tissue of the surgical incision, occurs within 90 days after the revision, and has at least one of the following:
 - purulent drainage from the deep surgical incision;
 - both of the following:
 - a deep incision that spontaneously dehisces, or is deliberately opened or aspirated by the Investigator and organism is identified by a culture or non-culture based microbiologic testing method which is performed for purposes of clinical diagnosis or treatment (e.g., not Active Surveillance Culture/Testing (ASC/AST) or culture or non-culture based microbiologic testing method is not performed:
 - at least one of the following signs or symptoms:

- fever(>38°C);
- localized pain, or
- tenderness.

Note: A culture or non-culture based test that has a negative finding does not meet this criterion.

- an abscess or other evidence of infection involving the deep incision that is detected on gross anatomical or histopathologic exam, or imaging test.
3. Full thickness skin dehiscence, defined as a separation of the closed incision at least through the subcutaneous tissue or deeper and at least one mm wide.
 4. Seroma or hematoma requiring drainage or surgery. The fluid accumulation will be classified as hematoma (bloody fluid) or seroma (clear or serous fluid) after drainage. The drainage may be percutaneous, an open technique at the bedside, or open surgical drainage.
 5. Skin necrosis is defined as the presence of necrotic tissue/skin eschar at the incision site that requires intervention with antibiotics, excision, and/or re-operation.

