4.11.2. Intervention Assessment

Information related to all interventions that are performed for an SSC will be documented at all post-surgery visits including unscheduled visits. Information collected will include but is not limited to:

- Date of intervention
- Type of interventions
- Types of interventions may include open surgical or percutaneous drainage, debridement, excision, or re-operation.

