4.15. Prohibited Procedures and Treatments

Subjects who undergo a subsequent surgery involving the initial TKA incision within 90 days must withdraw from the study.

Subjects who receive a subsequent TKA revision on the same knee within 90 days of the study revision must withdraw from the study prior to the procedure. Sites will record any SSCs that occur prior to the subsequent TKA revision and document the revision as the reason for the withdrawal from the study.

In the absence of an SSC, subjects receiving cross-over therapy after completing the original study treatment (ie, therapy from the arm in which the subject was not initially treated) must withdraw from the study.

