8.2. Analysis Sets

The following analysis sets will be used:

- ITT Analysis Set – The ITT (intention-to-treat) Analysis Set will consist of all randomized subjects. Subjects will be analyzed according to the treatment allocated at randomization.
- Safety Analysis Set – The Safety Analysis Set will consist of all randomized subjects who received any study-related treatment procedures. It is expected that all randomized subjects will be treated. All safety results will be presented based on the Safety Analysis Set. Subjects will be analyzed according to the study treatment they received immediately following the TKA revision.
- Modified ITT (mITT) Analysis Set – This set will include subjects in the ITT Analysis Set with the following: 1) an SSC on or before 90 days post-TKA revision or 2) no known occurrence of an SSC within 90 days of the TKA revision and was assessed at least once on or after the 90th day following the TKA revision. Subjects will be analyzed according to their randomized treatment assignment.
- Per-Protocol Analysis Set – This will include subjects in the mITT Analysis Set and had no disqualifying protocol deviation(s) that would impact the interpretation of the primary endpoint. The disqualifying protocol deviation(s) for exclusion from this set will be defined and documented in a blinded fashion prior to the final database lock by the Protocol Deviation Review Committee. Subjects will be analyzed according to their randomized treatment assignment.
- Modified Per-Protocol (mPP) Analysis Set – This will include subjects in the Per-Protocol Analysis Set excluding any subjects that received prohibited therapy as described in section 4.15 or any subjects that received alternative therapy following the study treatment period.

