5 ANALYSIS SETS

The following analysis sets are planned for this study:

- Safety Analysis Set: The Safety Analysis Set consists of all randomized subjects who received any study-related treatment procedures. Subjects will be analyzed according to the study treatment they received immediately following the TKA revision.
- ITT Analysis Set: The ITT (intention-to-treat) Analysis Set consists of all randomized subjects. Subjects will be analyzed according to their randomized treatment assignment.
- mITT Analysis Set: The modified ITT Analysis Set will include subjects in the ITT analysis set with the following: 1) who had any SSC on or before 90 days post TKA revision, or 2) had an assessment of SSC on or after 90 days post TKA revision and had no known occurrence of any SSC within 90 days post the TKA revision. Subjects will be analyzed according to their randomized treatment assignment.
- Per-Protocol Analysis Set: This will include subjects in the mITT analysis set who had no disqualifying protocol deviation(s) that would impact the interpretation of the primary endpoint. The disqualifying protocol deviation(s) for exclusion from this set will be defined and documented in a treatment-blinded fashion prior to the final database lock by the Protocol Deviation Review Committee. Subjects will be analyzed according to their randomized treatment assignment.
- Modified Per-Protocol (mPP) Analysis Set: This will include subjects in the Per-Protocol analysis set excluding any subjects who received prohibited therapy as described in Section 4.15 of the study protocol or any subjects that received alternative therapy following the study treatment period.

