8.5.1 Additional Analyses of Primary Endpoint

The below additional analyses (identified as sensitivity analyses in tables) described below may be performed for the primary efficacy endpoint, SSC:

- The primary analysis will be repeated using the actual revision type.
- A CMH test for SSCs stratified by randomized and actual revision type for the ITT, PP, and mPP will be included. Odds ratios and 95% confidence intervals will be presented.
- Summary of SSC events by type which include superficial SSI, deep SSI, dehiscence, seroma, hematoma, skin necrosis, or continued drainage based on the ITT, mITT, PP, and mPP analysis sets. Additionally, we will include SSC events of continued drainage that developed into SSIs.
- Summarize SSC events required intervention by type which include superficial SSI, deep SSI, dehiscence, seroma, hematoma, skin necrosis, and continued drainage based on the ITT, mITT, PP, and mPP analysis sets.
- For the septic and aseptic subpopulations, a Chi-square or Fisher's test as appropriate, will be performed within each actual revision type for SSC incidence rates between treatment groups based on the corresponding septic and aseptic mITT analysis sets.
- Perform a Fisher's exact test or Chi-square to compare the SSC incidence rates between two treatment arms without revision type stratification based on the mITT analysis.
- Multivariable analyses comparing the treatment groups with covariate adjustment where possible covariates might include (but not limited to) site, age, BMI, sex, type of revision (aseptic or septic), and subject comorbidities using logistic regression based on the mITT.

- Analyses comparing the heterogeneity of the treatment groups across clinical sites using logistic regression. (CMH) test stratified by clinical site based on the mITT.

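### The modified per-protocol set can drop subjects because they had the primary event: its alternative-therapy exclusion makes no exception for therapy given for an SSC

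*SAP*

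**What the plan says.** SAP 5 and Protocol 8.2 define mPP in the same way. It is the Per-Protocol set after two exclusions: (a) subjects with prohibited therapy under Protocol 4.15, and (b), in the SAP's words, "or any subjects that received alternative therapy following the study treatment period". Neither document defines alternative therapy.

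Protocol 4.15 contains rules of different scope:

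- The cross-over rule is conditional: "In the absence of an SSC, subjects receiving cross-over therapy after completing the original study treatment" must withdraw. It does not reach a subject who already has an SSC.
- The surgery rule is unconditional: "Subjects who undergo a subsequent surgery involving the initial TKA incision within 90 days must withdraw from the study".

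Surgery can be part of an SSC or its treatment. One SSC component in Protocol 4.11.1.1 is "Seroma or hematoma requiring drainage or surgery", and Protocol 4.11.2 says of SSC care: "Types of interventions may include open surgical or percutaneous drainage, debridement, excision, or re-operation".

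The primary comparison uses mITT (Protocol 8.3.4, SAP 8.5). SAP 8.5 also summarises SSC outcomes on mPP, and SAP 8.6 does so for any SSI and deep SSI. SAP 8.5.1 adds, among analyses to be labelled as sensitivity analyses in the tables: "A CMH test for SSCs stratified by randomized and actual revision type for the ITT, PP, and mPP will be included", with odds ratios and 95% confidence intervals.

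**The concern.** Exclusion (b) depends on care given after randomisation, and that care can be a response to the outcome being counted. Protocol 4.15 separates cross-over without an SSC from cross-over after one; exclusion (b) does not. A subject whose SSC was followed by alternative therapy would leave both the numerator and the denominator of the mPP rate. Exclusion (a) may have the same effect on a subject whose SSC was treated surgically, if surgery through the incision counts as prohibited therapy.

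At stake is whether the mPP result can be read as a check on the primary result. The trial is open-label, SSCs are investigator-assessed, and the therapy that counts as cross-over differs by arm, so equal removal from the two arms cannot be assumed.

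**Working it through.** **1. The plan's own figure.** Inputs from Protocol 8.4.2 and SAP 2.1: SSC rates of 33% septic and 6.9% aseptic at 50:50, a halving under ciNPT, two-sided 0.05, 80% power.

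- Pooled SOC rate: 0.5 × 33% + 0.5 × 6.9% = 19.95%, stated as 20%.
- Two-proportion formula with average rate 0.15: n = [1.96 × √(2 × 0.15 × 0.85) + 0.8416 × √(0.20 × 0.80 + 0.10 × 0.90)]² / 0.10² = 199 per arm.
- With the 0.0052 and 0.048 levels and the likelihood ratio test, power at 199 per arm is 80.1%.

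The sample size reproduces and is not in dispute.

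**2. Effect of removing event subjects.** Let p be the true SSC rate in an arm and q the share of its SSC subjects removed from mPP.

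- mPP rate = p(1 − q) / (1 − pq), which is below p whenever q > 0.
- mPP odds = p(1 − q) / (1 − p), so mPP odds ratio = true odds ratio × (1 − q ciNPT) / (1 − q SOC).

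The odds ratio is therefore unchanged when q is equal in the two arms and biased when it is not.

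**3. Equal removal, in whole subjects.** At planning rates 199 per arm gives about 40 and 20 events.

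- No removal: 40/199 = 20.1% and 20/199 = 10.1%; difference 10.1 points; OR = (20/179) / (40/159) = 0.44.
- Half of the event subjects removed in each arm: 20/179 = 11.2% and 10/189 = 5.3%; difference 5.9 points; OR = (10/179) / (20/159) = 0.44; uncorrected chi-square p = 0.039.

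**4. Range of assumptions.** The documents give no value for q. The table uses exact rates of 20% and 10% (hence 11.1% where step 3 has 11.2%), 199 per arm before exclusions, crude comparisons without the revision-type strata, and a pooled z-test at 0.048.

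| True rate SOC / ciNPT | q SOC / q ciNPT | mPP rate SOC / ciNPT | OR | Chance of p < 0.048 |
|---|---|---|---|---|
| 20% / 10% | 0 / 0 | 20.0% / 10.0% | 0.44 | 79.5% |
| 20% / 10% | 25% / 25% | 15.8% / 7.7% | 0.44 | 69% |
| 20% / 10% | 50% / 50% | 11.1% / 5.3% | 0.44 | 53% |
| 20% / 10% | 50% / 25% | 11.1% / 7.7% | 0.67 | 20% |
| 20% / 10% | 25% / 50% | 15.8% / 5.3% | 0.30 | 92% |
| 20% / 20% | 50% / 25% | 11.1% / 15.8% | 1.50 | 25% |
| 20% / 20% | 25% / 50% | 15.8% / 11.1% | 0.67 | 25% |

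Check on the unequal rows: 0.444 × 0.75/0.50 = 0.67, and 0.444 × 0.50/0.75 = 0.30. The last two rows compare with 4.8% when nothing is removed.

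**The case against.** **Consequences are limited.** No alpha, sample size or success criterion depends on mPP. SAP 8.5.1 introduces its analyses as ones that may be performed, ITT and Per-Protocol results stand beside mPP, and SAP 8.1 reports every subject excluded from mPP with the reason, so the removal of SSC subjects could be seen. All of this stands. It limits the harm but does not make the mPP estimate interpretable.

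**The bias need not run one way.** A reader might infer that only SOC loses events, since negative pressure is a new therapy only for SOC and, for ciNPT, "re-application of the Prevena[™] dressing is prohibited after the treatment period" (Protocol 4.10.3.1). The documents do not support that. Protocol 4.15 defines cross-over as therapy from the other arm, so a ciNPT subject later given a silver dressing may count too, and Protocol 4.10.3.3 records the dressing applied after ciNPT. The prohibition covers the Prevena dressing, not other therapies. The synopsis and Protocol 3.2 also describe the SOC arm as excluding other negative pressure therapy throughout the study. That sits awkwardly with supposing that SOC subjects would commonly be given it after an SSC. Nor does any section state that cross-over after an SSC is permitted; 4.15 is only silent on it.

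**Alternative therapy is undefined.** It might be read as no more than what 4.15 covers. Exclusion (b) would then add nothing to exclusion (a), so the wider reading is the natural one. How many subjects it reaches is unknown.

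**The remedy leaves some selection.** Keeping subjects whose SSC came first, while dropping event-free subjects who had alternative therapy, still depends on outcome. This stands, and it is a reason to read mPP as supportive only.

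**Conclusion.** The point holds for the mPP analyses. As written, exclusion (b) can remove subjects because they had an SSC. The surgery rule may do the same, but only if surgery is read as prohibited therapy. mPP rates are too low in any arm that loses events. Under equal removal the odds ratio, which is the measure SAP 8.5.1 presents, is unbiased; the cost is a smaller risk difference and lower power. Under unequal removal it is biased, towards or away from ciNPT. The size rests on assumed removal shares, and the direction cannot be determined from the documents.

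A reader might go further and conclude that the primary result is compromised. It is not: mITT keeps every subject with an SSC within 90 days as Occurred, and the superiority claim rests on mITT.

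**What to change.** In SAP 5 and Protocol 8.2:

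1. Define alternative therapy, and say whether surgery through the incision counts as prohibited therapy for this set.
2. Reconcile the mPP wording with Protocol 4.15, and with the description of the SOC arm in the synopsis and Protocol 3.2.
3. State that a subject is not excluded from mPP for alternative therapy or surgery that followed, or was given for, a documented SSC, and that such a subject stays in as Occurred.

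This changes an analysis set, not patient care. Record it in SAP 10; the SAP allows changes before the final database lock.

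The cost is a few sentences and a date comparison in programming. SSC onset dates (Protocol 4.11.1, 8.1.1), SSC intervention dates (4.11.2) and treatment removal dates (4.10.3.3) are already collected. One gap remains: 4.10.3.3 lists the type of dressing applied after removal but no start date, so the start of later therapy may have to be confirmed from source or concomitant records.

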6 INTERIM ANALYSIS

As stated in the protocol, an interim analysis will be conducted at information-time $t=0.5$, i.e., when approximately half the planned study subjects have had their primary endpoint assessed. The interim analysis will be performed at the $\alpha=0.0052$ level; if the p-value for the primary endpoint is < 0.0052 , the study will be stopped, and the null hypothesis rejected. Otherwise, the final analysis will be conducted at $\alpha=0.048$ (i.e., by constructing a 95.2% confidence interval) to preserve overall Type I error rate at 5%. These α values were chosen using an O'Brien-Fleming α -spending function assuming $t = 0.5$. The alpha levels that will be used at the interim and final will be calculated according to the precise information time at the interim analysis.

If warranted, based on the unblinded interim results, the final sample size may be increased using the appropriate statistical methodology as described in Chen et al. [2004]². Per Section 8.4.5 of the study protocol, it stated the increase to the final sample size would only occur if the interim results had a conditional power of success $\geq 50\%$, would be subject to the restrictions in Chen et al. [2004]², and

would not be considered statistically binding. However, the interim SAP further clarified that an increase to the final sample size could occur if the conditional power is below 50%. If the sample size is increased when conditional power is $\geq 50\%$, a type I error rate would not be inflated as mentioned in Chen et al. [2004]². If the sample size is increased when conditional power is $< 50\%$, an adjustment will be needed to control the Type I error. The adjustment was outlined in Section 7.3 of the interim SAP.

At the interim analysis, the rate of SSC for septic and aseptic revisions will be examined to confirm assumptions of the sample size calculations. In addition, the rate of SSC will be independently assessed for septic and aseptic revisions at the interim analysis to determine if a modification of enrollment from a 1:1 ratio of septic or aseptic revisions to focus on enrollment for either revision type is needed.

In the final analysis, the type I error rate ($\alpha=0.048$) for statistical significance will be used for the primary and secondary analyses using the O'Brien-Fleming method per study protocol.

Both, the interim SAP and the interim analysis results, will be included in the final clinical study report for this study.

Decisions and/or results from the interim analysis may affect the planned final data analysis. Therefore, this SAP may be amended after the interim analysis and before the final study database lock if necessary. Any changes will be documented appropriately in the corresponding Sections like "DOCUMENT HISTORY" and Section 10 "Changes from Planned Analysis".

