8.3.5. Analysis of Secondary Endpoints

Any SSI (superficial or deep) and Deep SSI will be analyzed in a similar fashion as the primary endpoint described in section 8.3.4. Superficial and Deep SSI will be analyzed separately and jointly; individual infection components will be summarized descriptively.

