2.1 Sample Size and Power

The primary endpoint of this study is the subject incidence of SSC. The incidence rates of SSC are different for septic and aseptic revisions; the assumed SSC rate is 33% for septic and 6.9% for aseptic. This study plans to enroll at least 50% septic revisions overall. These enrollment rates lead to an assumed pooled SSC rate of 20% in the SOC dressing arm.

Assuming an overall type 1 error rate of 0.05, with a two-sided hypothesis test, the study will have at least 80% power to detect a difference of 10% (50% reduction) in SSCs in the ciNPT arm with 199 subjects in each treatment arm, with one interim analysis at about 50% of the evaluable subjects for a total of 398

subjects using the likelihood ratio test. With an estimated 5%-10% loss, a non-binding interim analysis for superiority at approximately 50% of the evaluable subjects using O'Brien-Fleming method for monitoring boundaries, the planned sample size will be inflated for a potential loss of follow-up for a total of 440 subjects.

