4.2 Secondary Endpoints

4.2.1 Subject Incidence SSI

This secondary endpoint is the subject incidence of any Investigator-assessed SSI (superficial or deep) within 90 days of TKA revision in subjects treated with ciNPT as compared to SOC dressing. Superficial SSI and deep SSI are components of the primary endpoint. Subjects will be categorized using methods similar to those described in section 4.1 of this document.

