8.6.1 Analysis of Subject Incidence SSI

The proportion of subjects with each value of “Occurred” or “No occurrences” or “Incomplete-Follow-up” for SSI will be summarized, as applicable, by treatment arm based on the ITT, mITT, Per Protocol and Modified Per Protocol analysis sets.

Superiority Testing

The following hypothesis will be tested for superiority:

$$\text{Null } H_0: \Delta_{\text{ciNPT-SOC}} = 0$$

$$\text{Alternative } H_a: \Delta_{\text{ciNPT-SOC}} \neq 0$$

where $\Delta_{\text{ciNPT-SOC}}$ is the difference in the proportion of subjects in the ciNPT arm with at least one SSI and the proportion of subjects in the SOC dressing arm with at least one SSI.

For the combined population, a Cochran-Mantel-Haenszel (CMH) test stratified by randomized and actual type of revision (Septic, Aseptic) will be used to compare the SSI incidence rates between two treatment arms based on the mITT analysis set. The odds ratio and its asymptotic 95% confidence interval will be computed. This test is equivalent to the test of difference for the proportions.

For the septic and aseptic subpopulations, a Chi-square or Fisher’s test, as appropriate will be performed within each actual revision type for SSI incidence rates between treatment arms based on the corresponding mITT analysis set.

Additionally, figure(s) may be generated to display the results from the analyses of this endpoint graphically.

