8.6.2 Analysis of Subject Incidence Deep SSI

The proportion of subjects with each value of “Occurred” or “No occurrences” or “Incomplete-Follow-up” for deep SSI will be summarized, as applicable, by treatment arm based on the ITT, mITT, Per Protocol and Modified Per Protocol analysis sets.

The deep SSI subject incidence rates between two treatment arms based on the mITT analysis set will be compared in a similar fashion as the other endpoint described in section 8.6.1 of this document.

Additionally, figure(s) may be generated to display the results from the analyses of this endpoint graphically.

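### Both secondary infection endpoints get the primary's 0.048 level with no gate or order, so the three tests together carry about a 10–11% chance of a false significant result

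*SAP*

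**What the plan says.** SAP 2.1 plans the trial "Assuming an overall type 1 error rate of 0.05, with a two-sided hypothesis test" and sizes it on surgical site complications (SSC) alone. SAP 6 then fixes two levels. At the interim, "if the p-value for the primary endpoint is < 0.0052 , the study" is stopped; otherwise the final level is 0.048, chosen to keep the overall error at 5%. The same section adds that, at the final analysis, 0.048 "for statistical significance will be used for the primary and secondary analyses".

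SAP 8.6.1 gives any SSI its own null and alternative under the line "The following hypothesis will be tested for superiority". SAP 8.6.2 says that deep SSI "will be compared in a similar fashion as the other endpoint described in section 8.6.1 of this document". Protocol 8.3.5 says of both that they "will be analyzed in a similar fashion as the primary endpoint described in section 8.3.4".

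Neither document sets an order, a gate on the primary or a split of alpha for these two endpoints. The only gate and the only statement of strong control (SAP 8.5, the enrichment cases) concern the primary endpoint. The only waiver of multiplicity adjustment (Protocol 8.3.6) concerns exploratory endpoints.

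**The concern.** The secondaries fall between two treatments. They carry formal superiority hypotheses and a significance level, yet they are neither protected by a testing rule nor labelled descriptive. As written, a trial whose primary fails could still report an infection result as statistically significant at a pre-specified level. SAP 1 foresees use of these analyses in regulatory submissions and manuscripts, and infection is the component that readers would weigh most heavily.

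There is also a gap for an early stop. The final SAP sets the secondary level only for the final analysis and gives none for a trial that stops at the interim.

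**Working it through.** **1. The plan's 5%.** For two looks at t = 0.5, the primary's test statistics have correlation √0.5 = 0.707. Two-sided levels of 0.0052 and 0.048 correspond to |z| > 2.794 and |z| > 1.977. The bivariate normal probability of crossing at either look is 0.0500. The stated 5% is reproduced, and it is the error of the primary alone.

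**2. Upper references for three tests at 0.048.** If independent: 1 − (1 − 0.048)³ = 1 − 0.8628 = 13.7%. Bonferroni sum: 3 × 0.048 = 14.4%. Both are too high here, because the endpoints are nested: "Superficial SSI and deep SSI are components of the primary endpoint" (SAP 4.2.1).

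**3. Inputs.**
- From SAP 2.1: SSC 33% septic and 6.9% aseptic, so 0.5 × 33 + 0.5 × 6.9 = 19.95%, taken as 20%; 199 per arm.
- SSI share of SSC: not given for this trial. The only figure is from the retrospective hip and knee revision study in Protocol 1.3: 18.5/26.9 = 0.69 in its control group. This is the central assumption.
- Deep-SSI share of SSI: not given. Assumed 0.5 centrally, and about 0.25 to 0.85 as a range.

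**4. Allowing for nesting.** For an event of rate p_s contained in one of rate p_b, the correlation of the test statistics is √[p_s(1 − p_b) / (p_b(1 − p_s))]. Centrally, with SSC 20%, SSI 13.7% and deep SSI 7%:
- SSC and SSI: √[0.137 × 0.8 / (0.2 × 0.863)] = 0.80
- SSC and deep SSI: √[0.07 × 0.8 / (0.2 × 0.93)] = 0.55
- SSI and deep SSI: √[0.07 × 0.863 / (0.137 × 0.93)] = 0.69

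A trivariate normal with these correlations (4 million draws) gives, under the global null:

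| SSI / deep SSI (SSC 20%) | Any of three, final tests | Any of three, with interim on primary | Any of three in ciNPT's favour, final tests |
|---|---|---|---|
| 18% / 15% | 8.1% | 8.2% | 4.0% |
| 13.7% / 7% (central) | 10.5% | 10.7% | 5.3% |
| 10% / 5% | 11.2% | 11.4% | 5.6% |
| 4% / 1% | 12.7% | 12.9% | 6.4% |

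**5. Check at trial level.** Simulated trials with the two strata, 199 per arm and the stratified Cochran-Mantel-Haenszel test at 0.048 give 10.6% in the central case (400,000 trials).

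**6. Secondary significant, primary not.** This is the family rate minus the primary's own rate. Over SSI shares of 30–70% and deep-SSI shares of 25–85%, the simulated family rate at the final analysis is about 9.1–12.4%. Subtracting 4.8% leaves 4.3–7.6%, so about 4–8% two-sided. Counting only results in ciNPT's favour gives about 2.2–3.8%. If nearly all complications were deep infections (first row of the table), the two-sided figure would fall to 8.2 − 5.0 = 3.2%.

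**7. After a fixed sequence.** If any SSI is tested only after a significant primary, and deep SSI only after a significant any SSI, every false result under the global null requires a false primary. The family rate is then the primary's rate: 5.0% with the interim included.

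All of these figures count one test per endpoint. SAP 8.6.1 mentions stratification by both randomized and actual revision type and adds tests within each type, without saying which decides. That could only raise them.

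**The case against.** The strongest reply is that no stated figure is breached. A reader might infer that the plan promises 5% across all three endpoints and delivers twice that. The documents do not support this: SAP 6 derives the 5% from the primary's p-value over two looks, SAP 2.1 sizes the trial on SSC only, and SAP 8.5 limits strong control to the primary endpoint. That part of the reply stands in full.

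Direction also matters. A reader might take the whole 4–8% as false infection claims for ciNPT. About half of it would show more infection on ciNPT, and for the primary SAP 8.5 requires a lower ciNPT rate before superiority is declared. This stands too.

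Third, superiority wording alone proves little, since SAP 8.7.4 uses the same text for the exploratory 30-day endpoint; and many trials leave secondaries unadjusted. This stands only in part. What separates these two endpoints is the sentence in SAP 6 that assigns them a level for statistical significance, while Protocol 8.3.6 openly waives adjustment for the exploratory ones. Unadjusted secondaries are defensible when labelled supportive, and these are not so labelled.

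Finally, the interim SAP is a separate document that is not available here and may set a secondary level for an early stop. That gap can be asserted only for the final SAP.

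**Conclusion.** The point holds as a missing multiplicity rule for the secondaries. It is not an error in the primary's alpha, which stays at 5%. Under the global null, the family-wise chance of at least one false significant result among SSC, any SSI and deep SSI is about 10–11% two-sided, range about 8–13%, with roughly half favouring ciNPT. A secondary is significant without the primary in about 4–8% of null trials, or about 2–4% in ciNPT's favour. The sizes rest on the planning SSC rates, an even septic/aseptic mix, 199 per arm, and assumed SSI and deep-SSI shares. The structural finding does not depend on those shares. It should be settled before database lock, but it does not threaten the primary analysis.

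**What to change.** State in SAP 6 and 8.6 that any SSI is tested for significance only if the primary is significant, and deep SSI only if any SSI is significant, each at the level that applies at that analysis. Include the level for an early stop, unless the interim SAP already sets one, and name one stratification as decisive for each secondary test. Alternatively, drop the significance level for the secondaries and report their estimates, intervals and p-values as descriptive. Either is a wording change, and SAP 1 allows changes before the final database lock.

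The cost of the sequence is that a secondary cannot be claimed if an earlier test fails. Assume a uniform 50% reduction, with SSI half of SSCs and deep SSI half of SSIs. Power then falls from about 48–49% to 47% for any SSI and from 25% to 21% for deep SSI. With SSI at 30% of SSCs, deep-SSI power falls from 15% to 11%. The loss is larger if the effect is confined to infection, because unaffected components dilute the primary that opens the gate. If the sponsor thinks that likely, descriptive labelling may suit better. Estimates and intervals can be reported under either option.
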